2. CMP
3. Current Medications
4. Non-invasive blood pressure (SBP/DSP), weight
5. Concomitant Medications
6. Adverse Events (hyperkalemia, angioedema, acute kidney injury, sustained hypotension requiring cessation of drug)

30+ day phone call

1. 30 day readmission
2. Adverse Events

7.3 Informed Consent

Patients will be asked to consider participating in this study when they are being treated with intravenous furosemide infusion. During the consent discussion, prospective patients will be provided with a copy of the informed consent to read before making a decision. Once all patient questions have been answered, patients will be asked to sign an informed consent document prior to agreeing to enroll in the study.

7.3 Investigator Assurances

The PI is responsible for reviewing and authorizing all requests from others to obtain data from this database. Any additional users, known as Sub-Investigators, must submit to the PI a written request along with a signed Sub-Investigator Statement of Assurance. The PI is responsible for authorizing the release of data to Sub-Investigators and tracking these uses with a brief description of their activity.

The PI confirms no data from this database will be released without a written request from the sub-investigator and that the data provided will not contain identifiers unless consent from subjects has been obtained.

8.0 Monitoring Plan

- Review of all original signed ICFs (informed consent forms) for completeness and accuracy, including review of the version signed.
- Verify adequate documentation of the informed consent process and perform 100% SDV (source data verification) of the same.
- Source verify data entered into RedCap
- Verify compliance with current regulations and GCP (Good Clinical Practice) guidelines.
- Review all inclusion and exclusion criteria, SAEs and endpoints for 100% subjects.

8.1 Safety Monitoring

An internal Data Safety Monitoring committee will be comprised of Cleveland Clinic physicians who are not participating in the study as they do not rotate in inpatient clinical services or only practice in the intensive care settings (outside of the study cohort): [name] MD, Chair of the DSM committee, and members including [name] PharmD, and [name] MPH. Participant safety will be protected and monitored during the entire study period during their hospital admission and by 90-day phone calls to the patients. There will be a biweekly review of the safety and tolerability outcome measures by the study coordinator. These safety and tolerability outcomes and any other adverse events that occur will be recorded in the patient's electronic medical record. Any adverse events that occur will be investigated to identify possible etiology and relationship to study procedures and reported to the IRB and the DSM committee within 10 working days of their discovery, with the exception of any deaths, which will be reported within 5 working days of their discovery.

Data Base-Case Report Form Completion

Only site staff listed on the Signature and Delegation Log are authorized to enter data or make corrections to CRFs/CRF review will include review for legibility, completeness and consistency with source documents. CRFs should be completed on all subjects that have been randomized.

REFERENCES:

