5.2 Safety Endpoints

1. Initiation of dialysis or RRT.
2. Need for mechanical intubation or new initiation of positive pressure ventilation.
3. Need for IV vasoactive medications
4. ICU transfer
5. Death

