6.1.2 Serious Adverse Events

Adverse events are classified as serious or non-serious. A *serious adverse event* is defined as any adverse event occurring that results in any of the following outcomes:

- 1) Death
- 2) ICU transfer
- 3) Respiratory failure
- 4) Initiation of renal replacement therapy
- 5) A persistent or significant disability or incapacity

Important medical events that may not result in death, be life-threatening, or require hospitalization may be considered a serious adverse event when, based upon appropriate medical judgment, they may jeopardize the patient or subject and may require medical or surgical intervention to prevent one of the outcomes listed in this definition.

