6.1.3 Documenting and Reporting of Adverse Events

Adverse events reporting will begin from the time the patient is randomized until the subject has completed the final study visit.

For the purposes of this study, adverse events that are in the opinion of the investigator clinically significant will be tracked including hyperkalemia, acute kidney injury, and hypotension requiring cessation of drug.

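### Non-fatal serious adverse events reach the DSM committee no faster than non-serious ones: both share a limit of 10 working days

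*Combined protocol and SAP*

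**What the plan says.** Section 8.1 (Safety Monitoring) sets the reporting rule. Its scope is all adverse events: "Any adverse events that occur will be investigated to identify possible etiology and relationship to study procedures". They are then to be "reported to the IRB and the DSM committee within 10 working days of their discovery, with the exception of any deaths", and the deaths are those "which will be reported within 5 working days of their discovery". No other event has its own limit.

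Section 6.1.2 (Serious Adverse Events) states: "Adverse events are classified as serious or non-serious". Its list of serious outcomes includes "2) ICU transfer" and "4) Initiation of renal replacement therapy", together with death, respiratory failure, and lasting or significant disability. It also admits important medical events on medical judgment. It gives no reporting time.

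Section 6.1.3 gives the period over which events are collected, but no deadline: "Adverse events reporting will begin from the time the patient is randomized until the subject has completed the final study visit". It also limits tracking to events that the investigator considers clinically significant.

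Section 5.2 (Safety Endpoints) lists dialysis or renal replacement therapy, ICU transfer, IV vasoactive medication, death, and "Need for mechanical intubation or new initiation of positive pressure ventilation".

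**The concern.** The plan defines a serious class and then does not use it where speed matters. Apart from death, an event in that class may reach the DSM committee as late as an event outside it. Several of the events affected are ones by which the plan itself judges harm: start of renal replacement therapy and ICU transfer appear in both 5.2 and 6.1.2, and ventilatory support in 5.2 is close to respiratory failure in 6.1.2.

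At stake is how soon a body outside the study team hears of possible harm. Study drug is given for 4 days on a non-ICU floor. If notice may take longer than a course, patients already on treatment, and some who start later, can finish before the committee knows of the event.

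**Working it through.** The plan states no figure to reproduce; 10 and 5 working days are stipulated limits. The check asks whether another section gives a faster route, and then how long the window is.

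**1. Is there a faster route to the committee?**
- Section 6.1.2: a classification, with no time attached.
- Section 6.1.3: start and end of reporting, with no deadline.
- Section 8.0 (Monitoring Plan): serious adverse events reviewed in all subjects, with no timing.
- Section 8.1: a biweekly review of safety outcomes, done by the study coordinator and not by the committee. No committee meeting schedule is stated.

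The 10-working-day report is thus the only timed route by which the committee learns of a non-fatal serious event.

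**2. Length of the window.** Inputs: the limits in 8.1 and a 4-day (96-hour) course in 4.1 and 5.1.
- 10 working days = two calendar weeks = 14 calendar days, ignoring holidays.
- 5 working days = 7 calendar days.
- A patient on treatment at discovery finishes within 4 days, so before either limit.
- A patient who starts after discovery finishes before the limit if the start falls within 14 − 4 = 10 days (present limit) or 7 − 4 = 3 days (shorter limit).

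**3. How many patients?** Inputs: N = 85 and a single center (section 5.1). Neither enrolment duration nor accrual rate is stated, so duration is an **assumption**, shown as a range, with steady accrual and 30.4375 days per month. Counts cover both arms.
- Rate per day r = 85 / (months × 30.4375)
- Expected completions in the window = r × 14, or r × 7
- Of these, patients who start after discovery = r × 10, or r × 3

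| Assumed enrolment | r | Complete in 14 days | Of these, start after discovery | Complete in 7 days | Of these, start after discovery |
|---|---|---|---|---|---|
| 12 months | 0.233 | 3.26 | 2.33 | 1.63 | 0.70 |
| 18 months | 0.155 | 2.17 | 1.55 | 1.09 | 0.47 |
| 24 months | 0.116 | 1.63 | 1.16 | 0.81 | 0.35 |
| 36 months | 0.078 | 1.09 | 0.78 | 0.54 | 0.23 |

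With Poisson arrivals, the probability of 3 or more completions in 14 days is 0.63, 0.37, 0.22 and 0.10 for 12, 18, 24 and 36 months. An average of 3 needs enrolment within 85 / (3/14) / 30.4375 = 13.0 months, about 6.5 patients a month.

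**4. Effect of the shorter limit.** The maximum delay falls from 14 to 7 calendar days, which is half. Since 7 > 4, the limit still lies beyond one course.

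**The case against.** The strongest reply is that sections 6.1.2 and 8.1 do not conflict: one classifies events and the other sets a deadline. That is correct. This is a design choice, not a contradiction, and the documents contain no IRB or regulatory standard against which to call 10 working days too long. A reader might infer a breach of such a standard; the documents do not support that.

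The limit is also a maximum. Earlier reporting is allowed, and the 10 working days include the required look at cause and relationship to study procedures. This stands, although the clock starts at discovery, so late discovery adds to the delay.

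Other safeguards exist. Adverse events are recorded on each treatment day (section 4.1), the coordinator reviews safety outcomes biweekly, and monitoring covers serious events in every subject. The serious class is also used as a secondary endpoint. These count as safety measures, but none shortens the time to the committee.

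A reader might infer that serious events are handled like trivial laboratory findings. The broad definition in 6.1 invites this, but 6.1.3 narrows tracking to clinically significant events, so the fair comparison is with non-serious events.

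Finally, the plan states no stopping rule and no committee power to pause enrolment, so faster notice alone does not protect the next patient. That limits what the fix can achieve. It does not justify giving serious non-fatal events the slower limit.

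**Conclusion.** The point holds in a limited form. Non-fatal serious events share the 10-working-day limit of non-serious events, and no other section gives them a faster timed route to the committee. The limit is about 14 calendar days against a 4-day course, so further patients can complete treatment before the committee is told. The average number is about 1 to 3, resting on assumed steady enrolment of 85 patients over 12 to 36 months and on the full limit being used.

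Two stronger readings are tempting. One is that several more patients will routinely have been treated by then; that needs an accrual rate that the plan does not give, and an average of 3 needs enrolment to finish in about 13 months or less. The other is to divide 14 days by 4 and speak of 3.5 courses of exposure; patients are not treated back to back, so the ratio compares durations and does not count patients.

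This is an inexpensive improvement to oversight. It does not affect the analysis or the validity of the efficacy comparison.

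**What to change.** In section 8.1, widen the exception that now covers deaths so that it reads, in substance: deaths, and any other serious adverse event as defined in section 6.1.2, are reported to the IRB and the DSM committee within 5 working days of discovery; all other adverse events remain at 10 working days.

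This uses a limit and a definition that the protocol already contains. It halves the maximum notification delay to about 7 calendar days but does not bring it within one 4-day course. Need for IV vasoactive medication is a safety endpoint in 5.2 but is not on the 6.1.2 list, so it would move to the shorter limit only if it came with a listed event or was judged an important medical event. The sponsor should say whether that is intended.

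The cost is one sentence and some additional expedited reports. Their number cannot be estimated: the plan gives no serious adverse event rate, and 6.1.2 includes judgment-based events with no filter for relatedness.
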